10.3.2 Shipping Procedures

Blood collected into the appropriate tubes should be sealed, wrapped and placed in the specimen shipper kit and shipped on the same day they are drawn by Federal Express Priority Overnight courier using the return label provided in the kit. The green top tubes should be shipped at ambient temperature (no wet or dry ice) and the red and yellow top tubes should be refrigerated immediately and shipped at 2-8°C. Shipments must be timed to arrive during normal working hours and should be shipped in one box.

The laboratory will be open Monday through Friday to receive samples. Do NOT ship on Fridays or Saturdays, or the day before a legal holiday. Ship by overnight courier Monday - Thursday only to:

Immunologic Monitoring and Cellular Products Laboratory
University of Pittsburgh Cancer Institute
[name]
ECOG-ACRIN Study Coordinator
Hillman Cancer Center
[name]
[name]
[contact]
[contact]

Federal Guidelines for the Shipment of Blood Products: Sites should follow IATA regulations for Packaging UN3372 shipments. Please refer to FedEx guidelines.

An STS shipping manifest form must be generated and shipped with all sample submissions.

10.4 ECOG-ACRIN Sample Tracking System

It is **required** that all specimens submitted on this trial be entered and tracked using the ECOG-ACRIN Sample Tracking System (STS). The software will allow the use of either 1) an ECOG-ACRIN user-name and password previously assigned (for those already using STS), or 2) a CTSU username and password.

When you are ready to log the collection and/or shipment of the specimens required for this study, please access the Sample Tracking System software by clicking <https://webapps.ecog.org/Tst>

Important: Please note that the STS software creates pop-up windows, so you will need to enable pop-ups within your web browser while using the software. A

user manual and interactive demo are available by clicking this link:

<http://www.ecog.org/general/stsinfo.html>

Please take a moment to familiarize yourself with the software prior to using the system.

An STS generated shipping manifest form should be shipped with all specimen submissions.

Please direct your questions or comments pertaining to the STS to [contact].

Study Specific Notes

Generic Specimen Submission Form (#2981v2) will be required only if STS is unavailable at time of specimen submission. Notify the laboratory of the shipment by faxing a copy of the completed form to the laboratory. For specimen submissions to the IMCPL, notify the ECOG-ACRIN Study Coordinator by [contact] using the Specimen Shipment Requisition Form ([Appendix VIII](#)). If you are unable to get through to the laboratory by FAX, telephone the ECOG-ACRIN Study Coordinator at [contact] and provide the tracking number. Indicate the appropriate Lab ID# on the submission form:

- ECOG-ACRIN CBPF
- 0009= ECOG-ACRIN Immunologic Monitoring and Cellular Products Laboratory

Retroactively enter all specimen collection and shipping information when STS is available.

Rev. Add10

10.5 Use of Specimens in Research

Pathological materials will be distributed to investigators for central diagnostic review and immune bio-marker studies.

Specimens from patients who consented to allow their specimens to be used for future ECOG-ACRIN approved research studies, including residuals from the mandatory diagnostic review, will be retained in an ECOG-ACRIN designated central repository.

For this trial, specimens will be retained at the ECOG-ACRIN Central Biorepository and Pathology Facility and the ECOG-ACRIN Immunologic Monitoring and Cellular Products Laboratory.

Specimens submitted will be processed to maximize their utility for current and future research projects. Tissue processing may include, but not limited to, extraction of DNA and RNA and construction of tissue microarrays (TMAs). DNA, RNA, serum, and plasma (if appropriate) will be isolated from the submitted peripheral blood specimens.

Any residual blocks will be available for purposes of individual patient management on specific written request.

If future use is denied or withdrawn by the patient, the specimens will be removed from consideration for use in any future research study. Pathology materials may be retained for documentation purposes or returned to the site. All other specimens will be destroyed per guidelines of the respective repository.

10.6 Sample Inventory Submission Guidelines

Inventories of all samples submitted from institutions will be tracked via the ECOG-ACRIN STS and receipt and usability verified by the receiving laboratory. Inventories of samples forwarded and utilized for approved laboratory research studies will be submitted by the investigating laboratories to the ECOG-ACRIN Operations Office - Boston on a monthly basis in an electronic format defined by the ECOG-ACRIN Operations Office - Boston.

11. Correlative Studies

The results of these studies are for the purposes of the trial only and will not be returned to the site or reported to the patient.

Rev. Add10

11.1 Pathology Review (MANDATORY)

The appropriate representative tumor tissue samples will be forwarded to [name], PhD for central diagnostic review and classification to confirm the diagnosis. This is done as a retrospective review to determine the evaluability of the patient's data for analysis and to classify the tumor for analysis in the secondary aims. The results of the review are for the purposes of the trial only and will not be returned to the site.

11.2 Association of Inherited Variation with Immune Mediated Adverse Events and Response to Ipilimumab/Nivolumab

11.2.1 Correlative Study Design:

From all patients prior to receiving treatment on each arm of the study, buffy coats will be extracted from venous bloods and stored. Stored buffy coats will be shipped in batches on dry ice to the laboratory of [name] at the University of Pennsylvania for isolation of germline DNA and subsequent genotyping.

ECOG-ACRIN data items listed below will be requested for the analyses at University of Pennsylvania. The focus will be on the ipi/nivo treatment either as initial therapy or administered following dabrafenib/trametinib resistance. Measures of irAEs will include any irAE grade 3 or higher (yes/no); any gastrointestinal irAE (e.g. diarrhea, colitis; yes/no), any hepatic irAE (e.g. hepatitis, abnormal liver function tests; yes/no), any endocrine irAE (e.g. hypophysitis, hypopituitarism, yes/no) and any other irAE (yes/no)]. Information for survival outcomes will include duration of follow-up post treatment, vital status at time of last follow-up, and cause of censoring (death due to disease or otherwise), from which measures of survival status at one year (alive/dead/censored) and two years (alive/dead/censored) post treatment will be derived. Information on tumor response (complete remission/partial remission/stable disease/progressive disease) at 6 months will also be provided. Additional data on clinical covariates including sex, race/ethnicity, age at diagnosis, AJCC stage, ulceration (no/yes/unknown), performance status, LDH (normal/elevated), number of involved sites (1, 2-3, ≥4) and number of prior therapies will be requested.

11.2.2 Specific Hypotheses:

Multiple lines of evidence suggest that inherited genetic variation may play a role in response to immunotherapies, such as ipilimumab, but also in the development of irAEs. To address the hypothesis that inherited variation is a determinant of both response and irAEs, the University of Pennsylvania investigators have identified patients

treated on ipilimumab clinical trials from 10 academic contributing sites, two ECOG-ACRIN clinical trials and Bristol-Myers Squibb for a total of 716 and 1035 patients treated with 3mg/kg and 10mg/kg, respectively. We propose to determine the association of inherited variation with 1) irAEs and 2) overall survival at 1 and 2 years. In a discovery phase, we will perform candidate-based gene and pathway analyses of genes involved in lymphocyte activation, cytokines, cytokine receptors and within the MHC region, as well as an agnostic genome-wide SNP-based approach to discover novel genetic markers associated with our outcomes of interest. In a replication phase, we will replicate our findings in an independent sample set.

The aims of the whole project are described below. Biosamples and clinical information provided from EA6134 will contribute to the replication/validation step (Aim 3 below) for which a total of 950 melanoma patients treated with ipilimumab containing regimens are anticipated. It is expected that 210 of 300 patients from EA6134 will participate in Aim 3.

Aim 1: To determine the association of inherited genetic variation and immune-associated adverse events in patients with metastatic melanoma treated with ipilimumab containing regimens by completing: Aim 1a: Candidate-based gene and pathway analyses of genes involved in lymphocyte activation, cytokines, cytokine receptors and within the MHC region.

Aim 1b: An agnostic genome-wide SNP-based approach.

Aim 2: To investigate the association between inherited genetics and survival in patients with metastatic melanoma treated with ipilimumab containing regimens by completing.

Aim 2a: Candidate-based gene and pathway analyses of genes involved in lymphocyte activation, cytokines, cytokine receptors and within the MHC region.

Aim 2b: An agnostic genome-wide SNP-based approach.

Aim 3: To replicate genomic markers identified in Aims 1 and 2 in an independent sample set of patients treated with ipilimumab containing regimens and preliminary characterize their potential functional role.

Aim 3a: Replication of variation identified in Aims 1 and 2 as associated with irAEs and survival.

Aim 3b: Bioinformatic assessment of genomic markers.

11.2.3 Background:

Response to ipilimumab therapy can be quite durable with 24-30% of patients being alive at two years following treatment initiation; however, treatment with ipilimumab is associated with significant rates of immune related adverse events. Preliminary data from the ipilimumab/nivolumab combination suggests that response rates are greater and the responses occur more quickly and are more robust. Similarly, the irAEs associated with ipilimumab occur to a similar

extent with the ipi/nivo combination but can be more rapid and severe. It is therefore crucial to delineate both those at highest risk of irAEs and those that will most benefit from therapy with ipilimumab +/- nivolumab in order to direct this therapy to those most likely to receive benefit and avoid side effects and/or inform management. Of particular importance is identifying those patients who are unlikely to respond to the ipilimumab +/- nivolumab, who might be better treated with alternative agents or enrolled on other clinical trials. The lack of biomarkers (which includes genetic polymorphisms) for immunotherapies is well recognized, despite substantial efforts to date. As inherited polymorphisms do not vary and if they can serve as biomarkers, immune monitoring could be circumvented.

The genetic association study proposed by the University of Pennsylvania group is the first step in the identification of potential biomarkers. Multiple lines of evidence from other chemo- and immunotherapies as well from ipilimumab treatment, demonstrate the importance of inherited genetic variation to response and adverse events. Studies focusing on bevacizumab in breast and colorectal cancers have identified single nucleotide polymorphisms (SNPs) associated with a 60-90% increased overall survival; and polymorphisms in immunoglobulin G fragment C receptor (FcγRIIa), which plays a role in antibody-dependent cellular cytotoxicity, have been associated with response rates for cetuximab in colorectal cancer, trastuzumab in breast cancer, and rituximab in follicular lymphoma. Importantly, SNPs in and haplotypes of CTLA4 itself have been shown to be strongly associated (odds ratio (OR) 4.1, 95% confidence interval (CI) 1.2, 15 for the risk haplotype) with complete and partial response to treatment with ipilimumab in 152 patients with metastatic melanoma

[figure not shown]
[figure not shown]

Figure 1. GWA study of 113 melanoma patients treated with

A preliminary genome-wide association study of irAE and outcome for patients treated with ipilimumab was completed. DNA from 73 patients with resected stage IIIc/IV melanoma (25) treated with either 3 mg/kg (approximately 33% of patients) or 10 mg/kg ipilimumab at the H. Lee Moffitt Cancer Center was genotyped on the Illumina Human660W-Quad BeadChip. After quality control filters, the final sample set from MSKCC consisted of DNA from 44 melanoma patients. Because of differences in the definition of irAE (grade 2 and higher requiring

treatment vs. any grade 3 and higher) and types of patients (resected vs. non-resectable) between the two patient sets, samples from Moffitt were used to identify novel genetic associations (i.e. discovery phase) and samples from MSKCC were used to independently confirm observed top association (i.e. replication phase). In both sample sets, SNP markers with a call rate <0.98 were excluded from analysis.

The most significant observed associations for irAE were for rs2466176 ($P = 1.25 \times 10^{-6}$; OR = 4.84), rs416011 ($P = 4.24 \times 10^{-6}$, OR = 3.85) and rs375071 ($P = 6.97 \times 10^{-6}$; OR = 3.70) (Figure 1). rs2466176 maps to an intronic region of PEBP4, while rs375071 and rs2466176 are two closely-clustered SNP markers at 8q21.3 located between CNBD1 and DCAF4L2. Although associations did not reach genome-wide significance in this small sample set, the strength of the observed associations were quite impressive.

For response, two outcomes were examined 1) disease-free survival at the time of last follow-up; and (2) overall survival at time of last follow-up. Post-treatment follow-up at the time of analysis ranged from seven to 69 months. For relapse, the most statistically significant result ($P = 4.32 \times 10^{-6}$, OR = 3.6) was at rs6046009 in an intron SLC24A3, a plasma membrane sodium/potassium/calcium exchanger (Figure 2). In total, eight SNP markers at this locus had P values $< 1 \times 10^{-4}$ and were ranked within the top 50 hits. We observed the association with rs6046009 both in the Moffitt and MSKCC sample sets, suggesting that the association is not being driven by differences in a study-specific manner, i.e. by differences in outcome definition or individual treatment regimens. Additional loci on chromosomes 8, 15, and 16 have more than 2 SNP markers that surpassed a significance threshold of $P < 1 \times 10^{-4}$. Our preliminary data provide evidence that we will successfully identify novel genetic markers associated with ipilimumab-induced irAE and response.

11.2.4 Statistical Design:

Genetic associations with irAE status will be assessed using Fisher's exact test, one-degree-of-freedom genotypic trend test (analogous to the Cochran-Armitage test) or the two-degrees-of-freedom chi-squared test of independence at each individual SNP marker. Tests of association will be adjusted for age, sex, center or clinical protocol,

and dose as well as AJCC stage, ulceration, performance status, lactate dehydrogenase (LDH) level, number of involved sites, BRAF mutation status (when available) and number of prior therapies using logistic regression modeling assuming an additive genetic model. Within distinct genetic pathways or regions, P-values of individual SNP marker associations will be adjusted for multiple testing by controlling the false discovery rate (FDR).

Analysis for survival outcomes will occur within the framework of Cox proportional hazards analysis, otherwise similar to analyses described above for irAEs. In addition to adjusting for age at diagnosis, sex, center, clinical trial and dose, adjustment for variables potentially associated with prognosis including AJCC stage, ulceration, performance status, lactate dehydrogenase (LDH) level, number of involved sites, BRAF/NRAS/WT tumor mutation status, and number of prior therapies will also be made.

Study Power: For replication phase irAE outcomes, the study has 80% power to detect a per-allele RR of 2.90 or greater for SNP markers with a MAF of at least 0.10. For analysis of 2 year survival, the study has 80% power to detect a per-allele HR of 1.83 or greater for SNP markers with a MAF of at least 0.10. These detectable measures of effect compare favorably to point estimates we found in our small preliminary study.

11.3 Evaluation of the Utility of Circulating BRAF Levels in Determining the Response and Resistance to Either BRAF Directed and/or Immunotherapy in Patients with BRAF Mutant Melanoma

11.3.1 Correlative Study Design:

To define the dynamic and kinetic effects of systemic therapy on peripheral blood BRAF^{V600} mutation detection, we will test isolated PBL and serum from samples obtained from patients prior to receiving treatment on each arm of the study. As part of trial eligibility, patients will have been previously identified as being positive for a BRAF^{V600} mutation based on the results of the testing of their tumor tissue (either primary tumor or nodal/systemic metastasis) in a CLIA-approved laboratory for BRAF^{V600} sequencing analysis. Heparinized blood will be collected on each patient at baseline and every 6 weeks on both initial and crossover therapy and at the time of both RECIST defined progression and crossover to the alternative therapy. Blood samples will be shipped overnight at room temperature to the ECOG-ACRIN melanoma immunotherapy laboratory at the Pittsburgh Cancer Institute for ficoll to isolate PBMC. Samples will be labeled and stored at minus 80 for batch analysis.

11.3.2 Specific Hypotheses:

- a) To determine if changes in blood BRAF levels utilizing peripheral blood BRAF^{V600} mutational testing in patients with Stage IV BRAF mutant melanoma correlate with response and resistance to combination BRAF/MEK directed therapy.

- b) To determine if changes in blood BRAF levels utilizing peripheral blood BRAF^{V600} mutational testing in patients with Stage IV BRAF mutant melanoma correlate with response and resistance to combination immunotherapy.
- c) To compare the kinetics of peripheral blood BRAFV600 levels during response and resistance in groups of patients receiving BRAF targeted therapy or combination immunotherapy as initial therapy.
- d) To compare the kinetics of peripheral blood BRAFV600 levels during response and resistance to combination BRAF targeted therapy or combination immunotherapy in individual patients (initial treatment vs. crossover treatment).

11.3.3 Background:

[figure not shown]

Figure 1: Schematic of the BRAF^{V600} assay (A); (B) Results of direct sequencing; (C) Standard curve of BRAF assay.

[name], [name] and colleagues have developed and optimized an RT-PCR-based technique that takes advantage of an unique restriction enzyme site present in wild-type (WT) but not the mutant BRAF to enrich the sample for the mutant form initially and then inserts a restriction site into the mutant but not WT BRAF to allow for detection and quantification of mutant BRAF.¹ As outlined in our original description of this technique¹ and the second generation assay the protocol (Figure 1A) involves a series of PCR amplifications and restriction digestions that discriminate between WT and mutant BRAF at amino acid position 600. An initial RT-PCR is followed by digestion with TspR1 that preferentially digests the WT product but not the BRAF^{V600} PCR product. A second PCR using nested PCR primers with the digested 1st round PCR product as template follows. This PCR product may be subjected to sequencing using a nested oligonucleotide (Figure 1B), however, since the TspR1 digestion does not lead to complete elimination of WT BRAF, this PCR product is then subjected to a second TspR1 digest to further enrich for mutant BRAF^{V600}. Next, Real-Time PCR is performed on the second TspR1

digest product using primers designed to amplify BRAF^{V600E}. Purified first round PCR product with a known concentration is run through the assay along with test samples and is used to create a standard curve with each batched analysis of patient samples (Figure 1C). Using the standard curve the amount of end product is determined and BRAF^{V600E} levels are determined.

[figure not shown]

Figure 2: A) BRAF^{V600E} level is higher ($p < 0.0001$) in patients with tissue-detected BRAF mutation than in patients with Stage IV BRAF WT melanoma, and patients without melanoma (normal); B) BRAF^{V600E} level is borderline significantly higher ($p = 0.10$) among patients with Stage IV, BRAF mutant melanoma than in patients with Stage II and III melanoma with a "positive" BRAF level (≥ 10 pg).

In practice, the assay is highly sensitive and specific when used to analyze isolated PBMCs from patients with Stage IV melanoma. In particular, the sensitivity and specificity of the assay, using a cut off for positivity of 10 pg, is 93% and 100%, respectively (Figure 2A shows the box plot of BRAF values in patients with melanoma and known tissue BRAF status or people without melanoma). The average BRAF level in stage IV melanoma patients with tissue confirmed BRAF mutation is higher than the average BRAF level in patients with Stage II and III patients who have a positive blood BRAF level using the cutoff of ≥ 10 pg (Figure 2B), suggesting that the assay may reflect tumor burden. Lastly, when patients on BRAF inhibitor therapy were followed with serial sampling, the assay is reflective of disease response and disease progression. Specifically, BRAF levels generally reduce with treatment initiation and then increase at the time of or, in many cases, prior to radiographic progression.

[figure not shown]

Figure 3: Mean values of BRAFV600E levels prior to (PRE), during the first cycle(C1), or at the beginning of subsequent treatment cycles (C2-C7) in 12 patients treated with vemurafenib (A) and 6 patients treated with the combination of dabrafenib and trametinib (B).

A first generation peripheral blood BRAF assay had been utilized to follow serial circulating BRAF levels in several patients treated with either vemurafenib or the combination of dabrafenib with trametinib. In each patient, who had a known BRAF mutation detected in tissue from a CLIA approved laboratory, peripheral blood BRAF levels were

dabrafenib/trametinib and 100 second-line dabrafenib/trametinib treated) will be included in this analysis. Of these, we hypothesize 50% will have a favorable outcome (CR+PR and their blood BRAF level will decrease at least by 50% from the baseline value. The change in blood BRAF level between week 12 and baseline will be compared among patients with favorable outcome vs. no favorable outcome (SD or PD). Two-sample t-test will be used to compare the changes in the blood BRAF levels among responders (n=125) and non-responders (n=125). If the standardized difference is 1.38, there will be 85% power. This is based on a two-sided type I error rate of 0.05. If the normality assumption is not appropriate, Wilcoxon rank-sum test will be used in the analysis.

For assessment of association with resistance, the change in blood BRAF level on the most recent test done prior to documentation of RECIST defined disease progression on CT scan relative to the nadir level will be used. It is expected that a total of 200 patients (125 first-line dabraf/tramet and 75 second-line dabraf/tramet treated) will be included in this analysis. Of these we hypothesize that pre-progression samples will show a 50% increase from the nadir sample. The changes from the nadir sample will be summarized using the descriptive statistics. Also the proportion of patients who had at least 50% increase will be summarized. With a sample size of 200, 95% confidence interval will not be wider than 14%.

Aim 2b: The change in blood BRAF levels between week 12 (after initiation of therapy) and baseline (before BRAF/MEK therapy begins) will be used. It is expected a total of 250 patients (150 first-line ipi/nivo and 100 second-line ipi/nivo treated) will be included in this analysis. Of these, we hypothesize 5% will have a favorable outcome (CR+PR) and their blood BRAF level will decrease at least by 50% from the baseline value. The change in blood BRAF level between week 12 and baseline will be compared among patients with favorable outcome vs. no favorable outcome (SD or PD). Two-sample t-test will be used to compare the changes in the blood BRAF levels among responders (n=135) and non-responders (n=115). If the standardized difference is 1.38, there will be 85% power. This is based on a two-sided type I error rate of 0.05. If the normality assumption is not appropriate, Wilcoxon rank-sum test will be used in the analysis.

For assessment of association with resistance, the change in blood BRAF level on the most recent test done prior to documentation of RECIST defined disease progression on CT scan relative to the nadir level will be used. It is expected that a total of 200 patients (125 first-line dabraf/tramet and 75 second-line dabraf/tramet treated) will be included in this analysis. Of these we hypothesize that pre-progression samples will show a 50% increase from the nadir sample. The changes from the nadir sample will be summarized using the descriptive statistics. Also the proportion of patients who had at least 50% increase will be summarized. With a sample size of 200, 95% confidence interval will not be wider than 14%.

Aim 2c: Similar analyses as described under 2a/2b will be conducted in 150 patients with first-line therapy and 100 patients with second-line therapy in each group.

Aim 2d: The change in blood BRAF levels between week 12 and baseline will be compared between 150 patients receiving the first-line immune therapy vs. 150 patients receiving the first-line targeted therapy (at the time of response and progression as described in 2a/2b). A similar comparison will be made among 100 patients receiving second-line immune therapy vs. 100 patients receiving the second-line targeted therapy (at the time of response and progression as described in 2a/2b).

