2.3 Secondary Laboratory Objectives

- 2.3.1 Association of inherited variation with immune mediated adverse events and response to ipilimumab + nivolumab
 - 2.3.1.1 To determine the association of inherited genetic variation and immune-associated adverse events in patients with metastatic melanoma treated with ipilimumab containing regimens by completing candidate-based gene and pathway analyses of genes involved in lymphocyte activation, cytokines, cytokine receptors and within the MHC region and an agnostic genome-wide SNP-based approach.
 - 2.3.1.2 To investigate the association between inherited genetics and survival in patients with metastatic melanoma treated

- with ipilimumab containing regimens by completing candidate-based gene and pathway analyses of genes involved in lymphocyte activation, cytokines profile, cytokine receptors and within the MHC region and an agnostic genome-wide SNP-based approach.
- 2.3.1.3 To replicate genomic markers identified in the above aims in an independent sample set of patients treated with ipilimumab containing regimens and preliminarily characterize their potential functional role by completing replication of variation as associated with irAEs and survival and bio-informatic assessment of genomic markers.
- 2.3.2 To determine the utility of circulating BRAF levels in determining the response and resistance to either BRAF/MEK directed and/or combination immunotherapy in patients with BRAF mutant melanoma.
- 2.3.2.1 To determine if changes in blood BRAF levels utilizing peripheral blood BRAF^{V600} mutational testing in patients with Stage IV BRAF mutant melanoma correlate with response and resistance to combination BRAF/MEK directed therapy.
- 2.3.2.2 To determine if changes in blood BRAF levels utilizing peripheral blood BRAF^{V600} mutational testing in patients with Stage IV BRAF mutant melanoma correlate with response and resistance to combination immunotherapy.
- 2.3.2.3 To compare the kinetics of peripheral blood BRAF^{V600} levels during response and resistance in groups of patients receiving BRAF targeted therapy or combination immunotherapy as initial therapy.
- 2.3.2.4 To compare the kinetics of peripheral blood BRAF^{V600} levels during response and resistance to combination BRAF targeted therapy or combination immunotherapy in individual patients (initial treatment vs crossover treatment).
- 2.4 Secondary Patient Reported Outcomes Objectives

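### Circulating-BRAF plan (Section 11.3): 85% power corresponds to a standardized difference of about 0.38, not 1.38; the Aim 2b text contradicts itself, and no paired analysis is visible for the within-patient objective

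*Combined protocol and SAP*

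**What the plan says.** The statistical text for Aims 2a to 2d is at the end of Section 11.3.

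- **Aim 2a (targeted therapy), week 12.** The change in blood BRAF from baseline is compared by t-test between "responders (n=125) and non-responders (n=125"), two-sided 0.05, with a Wilcoxon rank-sum test as fallback. The power statement is "If the standardized difference is 1.38, there will be 85% power".
- **Aim 2b (immunotherapy), week 12.** The same power sentence is used for 135 responders and 115 non-responders among 250 ipilimumab/nivolumab patients (150 first-line, 100 second-line). The responder assumption reads "Of these, we hypothesize 5% will have a favorable outcome (CR+PR"). The reference sample is described as "and baseline (before BRAF/MEK therapy begins) will be used".
- **Aim 2b, resistance.** The population is 200 patients, given as "125 first-line dabraf/tramet and 75 second-line dabraf/tramet treated". This is the same wording as in Aim 2a.
- **Aim 2c.** The 2a/2b analyses are repeated in 150 first-line and 100 second-line patients in each group.
- **Aim 2d.** Week-12 changes are "compared between 150 patients receiving the first-line immune therapy vs. 150 patients receiving the first-line targeted therapy", and likewise 100 vs 100 second-line.

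Objective 2.3.2.2 and hypothesis (b) concern response and resistance to immunotherapy. Objective 2.3.2.4 and hypothesis (d) ask for kinetics "in individual patients (initial treatment vs crossover treatment"). Objective 2.3.2.3 and hypothesis (c) ask for the comparison between groups on initial therapy.

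**The concern.** A standardized difference of 1.38 is very large, and a comparison of 250 patients should detect far less. If the figure is wrong, readers of the plan are told that the substudy can find only very large differences.

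The Aim 2b problems affect what would be analysed. Followed literally, the resistance part of objective 2.3.2.2 would be addressed with patients on the other treatment. The week-12 change would be measured from a sample that does not mark the start of immunotherapy. The within-patient objective would have no matching analysis. These are prespecified secondary laboratory objectives, and corrections made after the assay data are seen would look post hoc.

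**Working it through.** **Power statement.** Inputs from Section 11.3: two-sample t-test, two-sided alpha 0.05, groups 125/125 and 135/115, power 85%, standardized difference d = 1.38.

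The noncentrality is d / √(1/n1 + 1/n2). Power is approximately Φ(noncentrality − 1.960), and the difference detectable with 85% power is approximately (1.960 + 1.036) × √(1/n1 + 1/n2). Exact values below use the noncentral t distribution.

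| | 125 vs 125 | 135 vs 115 |
|---|---|---|
| √(1/n1 + 1/n2) | 0.1265 | 0.1269 |
| Noncentrality at d = 1.38 | 10.91 | 10.87 |
| Power at d = 1.38 | > 99.99% | > 99.99% |
| Power at d = 0.38, normal approximation | 85.2% | 85.0% |
| Power at d = 0.38, exact t | 84.9% | 84.7% |
| d for 85% power, exact t | 0.380 | 0.382 |

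The stated 85% does not reproduce at 1.38. It does at 0.38, for both splits. In reverse, 2 × (2.996/0.38)² = 124.3, which rounds up to 125 per group, the size in Aim 2a. A difference of 1.38 would need only 2 × (2.996/1.38)² = 9.4, so 10 per group by the normal formula (exact t: 83.1% at 10, 86.8% at 11). A one-sided test, or the Wilcoxon test at its minimum asymptotic relative efficiency of 0.864, also has power of essentially 100% at 1.38. The ratio is 1.38/0.38 = 3.6.

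**Cross-check inside the protocol.** Appendix XVI (Aim 1) claims at least 85% power for d = 0.5 with 90 responders and 60 non-responders. There √(1/90 + 1/60) = 0.1667, the noncentrality is 3.0 and exact power is 84.6%. A smaller comparison in the same document therefore needs only about 0.5.

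**Responder rate in Aim 2b.** 5% of 250 is 12.5 patients; the test uses 135/250 = 54%. Both cannot hold. Section 1.5 reports 53% response at the top dose levels of the combination, and Appendix XVI expects roughly 50% responders by week 12.

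**Confidence interval.** The resistance paragraphs state a width of at most 14% at n = 200: 2 × 1.96 × √(0.25/200) = 13.9%. This reproduces.

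**Patients, baseline and comparison, side by side.**

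| Item | What the objective needs | What the analysis text gives |
|---|---|---|
| Aim 2b, week 12 | ipilimumab/nivolumab patients | ipilimumab/nivolumab patients (correct) |
| Aim 2b, resistance | ipilimumab/nivolumab patients | dabrafenib/trametinib patients |
| Aim 2b, baseline, second-line | sample before Arm D starts | sample before Step 1, so the change spans both treatments |
| Aim 2b, baseline, first-line | sample before Arm A starts | the start of Arm C, after immunotherapy, or no defined sample if the patient never crosses over |
| Objective 2.3.2.4 / hypothesis (d) | same patient, initial vs crossover therapy | Aim 2d: separate groups, 150 vs 150 and 100 vs 100 |

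Aim 2d as written is the group comparison of hypothesis (c).

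**The case against.** Several objections have weight.

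- **The 5% does not drive the power sentence.** A reader might infer that Aim 2b has 12 or 13 responders and is badly underpowered (85% power would need d of 0.86 to 0.89, and 0.38 would have 25 to 26%). The documents do not support this: the power sentence uses 135 and 115. The 5% is an inconsistent assumption, possibly a lost digit.
- **The wrong patients appear in one paragraph only.** A reader might infer that the whole immunotherapy aim is run on targeted-therapy patients. It is not; the week-12 paragraph names the right ones.
- **Objective 2.3.2.4 may not be wholly unserved.** The part of Section 11.3 just before the Aim 2a statistics was not available, so linking Aims 2a to 2d with hypotheses (a) to (d) rests on letters and content. Aim 2c covers first-line and second-line therapy, and swapped labels with an omitted paired test are plausible. The claim that the objective is unanswered goes too far. What stands is that no paired analysis appears in the text available.
- **The baseline problem is partly mitigated.** Blood is drawn at crossover (Sections 7.2 and 10.1), and Section 9.4 resets the tumor-response baseline at crossover. The data will exist, but the wording still needs correction.
- **Little depends on 1.38.** No sample size or stopping rule uses it, and it understates sensitivity. That limits the consequence but does not make the figure right.

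**Conclusion.** The power statement is wrong as written for both aims: at the planned sizes 85% power corresponds to about 0.38, and at 1.38 power is essentially 100%. The value 0.38 is a back-calculation that the documents never state, but it returns both the 85% and the 125 per group almost exactly. The 54% is likewise inferred, from 135/250.

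The contradiction over the responder rate, the patients in the Aim 2b resistance paragraph and the baseline wording are plain in the text. The missing paired analysis is less certain, because part of Section 11.3 was not available.

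The 0.38 holds only for the planned 250 patients. Appendix XVI reports crossover below expectation and projects about 150 ipilimumab/nivolumab patients with samples, at least 46 of them from Arm D. That is a different assay on the same trial's patients. If similar numbers applied here (an assumption), 90 vs 60 would need about 0.50 for 85% power, and 0.38 would have about 62%.

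These are secondary laboratory objectives. The text should be corrected before the assays are analysed; the 2-year survival comparison is unaffected.

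**What to change.** In Section 11.3:

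1. Replace 1.38 by 0.38 in Aims 2a and 2b, tied to the planned 250 patients, and restate the detectable difference for the samples actually available (for example about 0.50 at 90 vs 60).
2. Make the Aim 2b responder rate agree with 135/250, about 54%.
3. In the Aim 2b resistance paragraph, name the first-line (Arm A) and second-line (Arm D) ipilimumab/nivolumab patients and give their expected numbers.
4. Define baseline as the sample before the start of that line of therapy: Step 1 baseline for Arm A, Step 2 baseline for Arm D.
5. For objective 2.3.2.4, add a paired comparison (paired t or Wilcoxon signed-rank) of each crossover patient's change on initial and on crossover therapy, with the number of pairs updated from the planned 100 to actual crossovers. Keep the between-arm comparison under Aim 2c.

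The cost is an amendment to the text. Blood is already scheduled before treatment, every six weeks on initial and crossover therapy, at crossover and at progression, so no new samples are needed.
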